3.0 Design

Overview. This is a study examining the effects of TI on brain activity as measured by fMRI BOLD signals (Aim 1), and the effects of TI-related changes in deeper brain region activity on cognitive functions. Both aims build on our preliminary results showing focal changes in BOLD signals resulting from TI. In Aim 1, we will first establish the effects of TI on BOLD signals, then show that

these are not confounded with the high frequency carrier signal effects alone, and then show how TI can manipulate activity can propagate across brain networks to influence functionally connected brain regions. In Aim 2, we apply TI to stimulate a deeper brain region, the dorsal anterior cingulate cortex, to resolve longstanding questions about its causal role in cognition. We anticipate recruiting 200 subjects, allowing for attrition to achieve our goal of 30 subjects for each individual study below.

Subjects will spend 2-3 hours for the session and be paid \$35/hour.

Aim 1: Test and characterize the effects of TI on the fMRI BOLD signal

In all studies, we will administer the Stimulation experience scale before starting the stimulation and after the stimulation session is complete. Subjects will also be asked periodically to rate any discomfort on a scale of 1-5 (5=highest discomfort), and indicate the location and qualities of any discomfort.

Study 1.1. Test the effect of TI in NAcc, controlling for the effects of high frequency

stimulation. Healthy subjects (n=30) will be placed in the fMRI scanner and administered the same protocol used to generate our pilot results in Figure 2. Specifically, subjects will have two pairs of carbon fiber electrodes attached with conductive gel, at {F9, F10} and {Fp1, CPz}. They will receive one 8-minute block of stimulation at 2mA per electrode pair. The stimulation sequence will be 2 minutes on, 2 minutes off, 2 minutes on, and 2 minutes off with 30 second ramp up and ramp down beginning at the start of each 2-minute period. The first block will apply active TI stimulation with 2000Hz in one channel and 2020Hz in the other channel. The second block will be a sham TI stimulation, identical to the first block but with the “on” condition immediately ramping down as soon as it reaches 2mA after ramp up. The third and fourth blocks will be identical to the first and second blocks, except that both electrode pairs will stimulate at 2000Hz, resulting in a “NO-TI active” and “NO-TI sham” conditions. The order of blocks, and whether the “on” or “off” condition occurs first within a block, will be counterbalanced across subjects.

Study 1.2. Test effect of varying TI beat frequencies on BOLD inhibition vs. activation. In the same left NAcc region, also with n=30 subjects, we will repeat Study 1.1, but instead of the NO-TI condition with a zero Hz beat frequency, we will replace it with a 5Hz beat frequency (2000Hz and 2005Hz in the two channels). Likewise the 20 Hz beat frequency condition will be replaced with 30 Hz (2000Hz and 2030Hz stimulation). We will then compare the degree of BOLD activation for 5 vs. 30 Hz beat frequencies as in Study 1.1.

Study 1.3. Confirm effect of TI on the dorsal ACC, around MNI 0, 30, 30. We will repeat Study 1.1, but targeting the dorsal ACC (n=30 subjects), to confirm we can activate it with 20Hz TI. Instead of zero Hz as in Study 1.1, we will use the frequency from Study 1.2 that is found to produce the strongest BOLD activation other than 20 Hz, which will be 5Hz, 30Hz, or 40Hz. We may find that certain beat frequencies are futile, we may select an alternative beat frequency in the range of 1 to 100 Hz.

Aim 2: Identify causal effects of dorsal anterior cingulate cortex (dACC) on cognition

Study 2.1. Test whether 20Hz TI in the dACC enhances or disrupts cognitive control. For this, n=30 human subjects will be placed in the fMRI scanner to perform a flanker task(Eriksen & Eriksen, 1974), in which subjects must indicate whether the central arrow points left or right. The

trials will be 50% congruent (“<<<<” and “>>>>”) and 50% incongruent (“<<><<” and “>><>>”) trials. Previous work shows not only elevated reaction time and error rates for incongruent trials, but also a “Gratton effect” in which RT and error rate (as well as dACC activity) are even more elevated for incongruent trials that follow a previous congruent trial (Botvinick et al., 1999). This is arguably because cognitive control-related activity in the dACC prior to the start of the trial was lower, thus requiring more cognitive control-related activation as a reaction to the incongruent task stimulus(Botvinick et al., 1999). We will test whether the Gratton effect is reduced by TI to the dACC in the scanner, and whether this is accompanied by increased baseline dACC activity due to TI. Subjects will be divided into two groups. One will receive 2 consecutive eight-minute blocks of TI stimulation (2000 and 2020 Hz in the two electrode pairs, or alternatively the most effective beat frequency identified in Aim 1) to dorsal ACC, followed by 2 eight-minute blocks with no-TI stimulation, as subjects perform the flanker task in the fMRI scanner. The second group of subjects will undergo an identical procedure, except that the first two blocks will be no-TI stimulation, followed by 2 eight-minute blocks of TI stimulation. In all subjects, blocks 1 and 3 will include the Flanker task, and blocks 2 and 4 will include the visual search task of Magno et al., (2006). The visual search task will provide the data needed for Study 2.2.

Study 2.2. Test the causal role of dorsal anterior cingulate in avoidance. We will apply TI stimulation as in Study 2.1 to the dorsal ACC with subjects in the fMRI scanner, and for efficiency, we will run this task on the same subjects as Study 2.1 concurrently and without leaving the scanner. Subjects will perform the task of Magno et al. (2006), during blocks 2 and 4 of the sessions described in Study 2.1. Specifically, subjects will perform a visual search task, identifying “target present” or “target absent” within a short deadline. There are two trial types, easy (few non-targets) and hard (many non-targets). They gain +1 reward for correct responses (converted to cash after the session), -1 reward for errors, and they can also skip the trial for 0 reward to avoid risk. Previous work shows dorsal ACC activity only when subjects skip the trial to avoid the risk of an error, but anterior insula activity occurs instead when subjects choose to respond and then make an error (Magno et al., 2006).

Study 2.3. Test the causal role of the dorsal ACC in foraging decisions. Using the TI stimulation of Study 2.1 with humans subjects in the scanner (n=30), subjects will perform a foraging and difficulty task(Shenhav et al., 2014) to adjudicate between competing theories of dorsal ACC, whether it drives foraging or reflects task difficulty. Subjects will be divided into two groups as in Study 2.1 and will perform the task of Shenhav et al. (2014)(Shenhav et al., 2014) during 4 eight-minute blocks, with TI and no-TI conditions in the scanner as in Study 2.1 for each of the two groups. In the task, subjects must decide whether to accept playing a gamble with known probabilities or forage to find a better gamble with more favorable probabilities. The relative value of foraging (RVF), i.e. the difference in expected value for playing the gamble vs. foraging, varies between an easy decision (large positive or negative RVF) or a difficult decision (near-zero RVF).

Risks of participation and mitigation of risks:

Subjects may feel uncomfortable completing the interview. For instance, there are questions about whether they may be pregnant, surgical history, and about the existence of tattoos and piercings on the body. They may decline to answer specific questions or decline to continue participating.

complete scan for any clinical purpose. If there is an abnormality, the scan, the MRI technician, or the researcher may not detect it. If the technician or researcher suspects a possible abnormality, the scan will be sent without any participant identifiers to a neuroradiologist for further review. If the neuroradiologist recommends further action, the subject will be notified.

MR imager: MRI has not been shown to produce health problems in normal, healthy individuals. The imager DOES NOT produce ionizing radiation, which is radiation associated with conventional radioactive sources, such as x-rays, radioactive iodine, uranium, or other substances. No medication, needle stick, or injections of drug or contrast agents are involved. There are hundreds of imagers of this type used in the U.S. and abroad, both to assist doctors in clinical diagnoses and for research. To view a copy of the Food and Drug Administration safety guidelines for MR imagers, subjects may simply ask the MRI operator.

Because of the strong magnetic fields used for MR imagers, persons who have magnetic life-support devices (e.g., pacemakers and aneurysm clips), metal prostheses or other metallic objects (e.g. cochlear implants, steel pins implanted to help repair and strengthen broken bones, metal fragments from previous injuries) cannot participate in this research. Subjects will be screened for MR contraindications

The radio frequency energy used in this exam has produced burns (most of them minor) in about one in a million cases. If subjects feel any burning sensation they will immediately inform the staff, so that the scan can be stopped.

MRI may be harmful to an unborn child. If subjects are of childbearing potential (that is, if subject is a woman with sexual partner(s) and do not use an adequate birth control method), they must be excluded. Reliable birth control (i.e. oral, implanted, or barrier methods) should be used by all participants and/or their sexual partner to prevent pregnancy while participating in MR imaging. If subjects find that they were pregnant while participating and undergoing MRI, you should notify their physician immediately. If subjects use an IUD for birth control they will be excluded unless they can document the model of the IUD and we can verify its safety for the MRI environment. Pregnancy should be self-reported, and a pregnancy test will not be administered.

While there is no evidence of increased risk with multiple scans, the risks associated with multiple scans are not known. The IUB imaging center is adopting an arbitrary maximum of 40 hours of scanning time per individual per year and the time involved in the present study is well below that limit.

Though uncommon, there is also the risk that the imaging procedure may result in nausea, dizziness, sweating, or headaches. Individuals who suffer from migraines may be more susceptible to these side effects as a result of the noise level inside the scanner. These symptoms are generally temporary, and the scan can be stopped at any time if you begin experiencing discomfort.

Brain stimulation:

1. Mild physical discomforts: Approximately 66% of participants who receive this kind of stimulation experience mild physical discomforts that are short-lived, such as tingling, itching, redness, or mild burning sensations on the skin under the pads. Some participants have also reported occasional mild headaches and fatigue. There is also a risk of seeing flashing lights.

These effects are mild, short lived, and benign. The electric current is very mild and is approximately 1000 times smaller than the average static electric shock one might receive touching a door knob or light switch after walking on a carpet with socks. While it is rare, some participants may experience a stronger unpleasant sensation. If subjects

experience any discomfort or wish to stop the experiment, subjects will let the experimenter know and the procedure will be stopped immediately.

2. Long term effects: Long term effects of exposure are largely unknown, though no long term adverse effects have been reported from any previous study. As a precaution, the stimulation will not last longer than 20 minutes continuously at one time.

3. Medical precautions: Though a significant adverse event has never been reported with similar brain stimulation procedures, there theoretically may be a risk to persons with conductive metal (i.e. implants) in their head, and to persons who suffer from migraines, epilepsy, or other neurological syndromes. If subjects have any of these conditions they may be ineligible to participate in this study. Also, subjects may be ineligible to participate in the study if they have a history of seizure disorder, history of cognitive impairment, symptoms of psychosis or if you are taking medications for cancer, attention deficit hyperactivity disorder (ADHD), autoimmune deficiency syndrome (AIDS), or other mental illness.

These risks will be managed by trained researchers; at least one will always be present when the machine is operating. The researcher will stop the experiment if they experience discomfort that you do not wish to tolerate. Furthermore, the stimulator does not transfer current greater than 3 mA per electrode pair, which is still, relatively, a very small current.

Other risks

There is a small risk of boredom during the session. Subjects can withdraw themselves if they do not wish to continue.

There is also a small risk of loss of confidentiality. We will minimize that risk by storing the records in secure (locked or password-protected) locations. Electronic data will be identified only by the subject's study ID number, with the master list linking the subject ID to identifiable information stored on paper. Electronic data will be stored on the PI's servers or on Indiana University servers. All systems will have at least password protection. Paper data will be stored in locked cabinets inside a locked room.

Study procedure summary

Days before the session:

- Recruitment (via paper flyers and digital ads)
- Pre-screening (via phone)

Day of session:

- Consent
- Fill out questionnaires
 - MR safety screening
 - Demographic form
 - Edinburgh handedness inventory
 - WHODAS 2.0
 - PHQ-9
 - GAD-7
 - Stimulation experience scale (SES)
- Subjects randomized to receive active vs. sham stimulation first, using an alternating list, in which successive subjects are assigned to the conditions of active first, then sham first, then active first etc.
- Brief cognitive task explanation and practice (Aim 2 only)
- Attach electrodes (day of session, in MR facility)
- Scanning while undergoing TI (and if Aim 2, performing cognitive tasks) (day of session)
 - Brief stimulation scale

- Multiple scanning and stimulation runs, where each stimulation run is followed by administering the brief stimulation scale
- Subject removed from scanner, electrodes removed
- SES repeated
- Subject paid and dismissed

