In a set of pilot subjects (Modak et al., 2024), we applied 2mA per each channel of TI stimulation using the Soterix Interferential Neuromodulation System (Soterix Medical, Inc.), via carbon fiber electrodes while subjects were scanned with whole-brain fMRI (Fig. 2). Frequencies were 2000 Hz and 2020 Hz, for a 20Hz beat frequency. We aimed to target the left nucleus accumbens, and our finite element simulations predicted an optimal electrode placement with one channel at {F9, F10} in the EEG 10-10 locations and the other channel at {Fp1, CPz} (Fig. 2 top). Each subject received alternating 2 minutes on / 2 minutes off stimulation, with 30-second current ramp up and down. Sham stimulation consisted of current ramp up followed immediately by current ramp down, to control for initial scalp tingling(Gandiga et al., 2006). The sham stimulation will be controlled by the experiment script on a computer and is designed so that subjects will not be able to discern the difference between active and sham stimulation; the subject's experience will be the same, involving mild tingling in some subjects. Subjects received four sets of on/off stimulation for each of stimulation and sham conditions, with the order of on vs. off first counterbalanced. The results (Fig. 2 bottom) show increased BOLD signal in the region predicted by the finite element simulation. Moreover, when we changed the frequencies to be the same (i.e. 2000 Hz in both channels, the high frequencies remained, but the TI beat frequency was abolished. In 8 pilot subjects, the BOLD activation seen in Fig. 2 (bottom) was likewise abolished, which suggests that TI and not the high frequencies *per se* are essential for the BOLD activation observed. Our pilot subjects tolerated the stimulation well and revealed no substantial safety concerns. These pilot results will be tested more fully in **Aim 1**.

[figure not shown]

Fig. 2. Top: Finite element simulation prediction of TI effect of 2000Hz vs. 2020Hz at {F9, F10} and {Fp1, CPz}. Bottom: Increased fMRI BOLD effect due to TI in our pilot subjects (TI stimulation minus sham, Z statistic across n=16 subjects).

Characterizing the effect of TI on fMRI BOLD and cognition

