The most fundamental open question here is how TI may influence activity as measured by the fMRI BOLD signal. New work suggests TI at 5 Hz beat frequency may suppress BOLD activity (Violante et al., 2023), but our pilot data with a 20 Hz beat frequency suggests TI may increase BOLD activity. **Study 1.1** will test whether a 20Hz beat frequency TI may increase BOLD activity. Second, it remains to be established whether the BOLD effects are due to the beat frequency rather than an overlap of two high frequency signals of the same frequency. **Study 1.1** also includes a comparison between 20Hz beat frequency TI vs. a control condition of zero Hz beat frequency, i.e. when the two electrode pairs have the same frequency (2000Hz). Third, because theoretical work suggests that higher beat frequencies may cause more neural excitation(Cao et al., 2020), we will directly compare 5 Hz TI vs. 20 Hz TI in **Study 1.2**. Fourth, it remains to be established how specifically TI can target various deep brain regions. In preparation for Aim 2, we will test how well TI at 20 Hz can focally target the dorsal anterior cingulate cortex (around MNI 0, 30, 30) (**Study 1.3**).

Resolving long-standing debates about the role of dorsal anterior cingulate cortex

The causal role of several deep brain regions in cognition remains unresolved. This is because we have lacked a method to temporarily and non-invasively disrupt deep brain regions without also disrupting the overlying cortex, which leads to confounds. This limitation applies to transcranial direct and alternating current stimulation, and transcranial magnetic stimulation, even with deep TMS coils(Harmerlech et al., 2021). Transcranial focused ultrasound holds some promise(Kubanek, 2018) but can only minimize the superficial stimulation, not eliminate it.

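### Study 1.1's zero-beat control matches the current delivered, but the relative phase and lead polarity of its two 2000 Hz channels are not stated, so a matched carrier field at the target is not assured

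*Combined protocol and SAP*

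**What the plan says.** The heading of Study 1.1 in 3.0 Design gives the purpose: "Test the effect of TI in NAcc, controlling for the effects of high frequency" stimulation. The overview of 3.0 Design says that Aim 1 will show the BOLD effects are not explained by the carrier alone. 2.0 Background names the comparator as "a control condition of zero Hz beat frequency, i.e. when the two electrode pairs have the same frequency (2000Hz".

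In the TI condition, "The first block will apply active TI stimulation with 2000Hz in one channel and 2020Hz in the other channel". The current is the same throughout ("They will receive one 8-minute block of stimulation at 2mA per electrode pair"), and so are the electrode positions ("at {F9, F10} and {Fp1, CPz"). For the control, "The third and fourth blocks will be identical to the first and second blocks", "except that both electrode pairs will stimulate at 2000Hz". Each active block has its own sham. Block order, and whether a block starts on or off, are counterbalanced across subjects.

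The pilot section of 2.0 Background treats the carrier as unchanged when both channels run at 2000 Hz: "the high frequencies remained, but the TI beat frequency was abolished". It reports that the BOLD activation disappeared in 8 pilot subjects and takes this as evidence that the beat is essential.

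The documents do not state the relative phase of the two channels, which lead of each pair is positive, whether the outputs are phase-locked, or the modelled carrier field at the target in the zero-beat condition.

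**The concern.** At the electrodes the carrier is indeed the same in both conditions. In tissue it need not be. With 2000 and 2020 Hz, the relative phase of the two fields sweeps a full cycle 20 times a second, so reinforcement and cancellation average out. With 2000 Hz in both channels and a fixed phase, the fields form a standing pattern, which reinforces or cancels at a given place according to phase and polarity.

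Near antiphase, the control may have little carrier at the target. A missing BOLD response would then fit loss of the carrier as well as loss of the beat, and the pilot result is open to the same reading. Near in-phase, the control has more carrier power than TI, which could mask a true beat effect. The sham blocks do not resolve this, because they omit the sustained stimulation in which the mismatch arises. Counterbalancing block order does not remove it either if phase and polarity are the same in every subject.

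**Working it through.** The plan gives no carrier-field figure, so there is none to reproduce.

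**Inputs from 3.0 Design, Study 1.1:** TI at 2000 and 2020 Hz (beat 2020 − 2000 = 20 Hz); control at 2000 and 2000 Hz (beat 0); 2 mA per pair and the same montage in both; n = 30.

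**Assumed, because not stated:** relative phase φ from 0 to 180 degrees; field ratio r = a2/a1 from 0.25 to 1; angle θ between the two fields from 0 to 90 degrees; phase-locked channels (relaxed in step 4).

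**1. Mean-square carrier field along one direction,** with channel amplitudes a1 and a2:
- TI: (a1² + a2²)/2, because the cross term cycles at 20 Hz and averages to zero.
- Control: (a1² + a2²)/2 + a1·a2·cos φ.
- Power ratio, control to TI: 1 + 2r·cos φ/(1 + r²). The RMS ratio is its square root.

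**2. Equal fields (r = 1).** The power ratio is 1 + cos φ. TI itself peaks at a1 + a2 once per beat, so the peak ratio is |cos(φ/2)|.

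| φ (degrees) | Power | RMS field | Peak field |
|---|---|---|---|
| 0 | 200% | 141% | 100% |
| 60 | 150% | 122% | 87% |
| 90 | 100% | 100% | 71% |
| 120 | 50% | 71% | 50% |
| 180 | 0% | 0% | 0% |

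**3. Unequal or non-aligned fields.**
- r = 0.5, aligned: 2r/(1 + r²) = 1/1.25 = 0.8, so power is 20% to 180% (RMS 45% to 134%).
- r = 0.25, aligned: 0.5/1.0625 = 0.47, so power is 53% to 147%.
- Total power at angle θ: 1 + 2r·cos θ·cos φ/(1 + r²). At 60 degrees this is 50% to 150% for r = 1 and 60% to 140% for r = 0.5.
- Orthogonal fields: total power is 100% at every phase. For equal orthogonal fields, power along the diagonal still runs from 0% to 200%.

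A numerical superposition of the two sinusoids matched the total-power formula in all 30 combinations of r, θ and φ tried.

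**4. Channels not phase-locked.** With a frequency mismatch Δf, the mean of the cosine term over a 120-second on-period is at most |sin(πΔf·120)/(πΔf·120)|, ignoring ramps. At Δf = 0.05 Hz that is 6 whole cycles, so the mean is 0. At Δf = 0.01 Hz it is 1.2 cycles, so the bound is 0.156 and the power ratio for equal aligned fields stays within 84% to 116%.

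**5. Other beat frequencies.** At 5, 20 or 30 Hz the cross term also averages to zero, so mean-square field is (a1² + a2²)/2 in each case. Study 1.2's comparison of 5 with 30 Hz is therefore matched on carrier power.

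**6. Effect of a lead swap.** Reversing one pair shifts φ by 180 degrees and changes the sign of cos φ. With half the subjects each way and φ otherwise stable, the mean power ratio is 1. For example, at r = 1 and φ = 60 degrees, (150% + 50%)/2 = 100%.

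**The case against.** The strongest reply is that the carrier is controlled: electrodes, current per pair, timing and sham are the same in both conditions. This stands for delivered current. It does not extend to the field at the target, which is what the claim about the nucleus accumbens needs.

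A second reply is that Study 1.1 is not the only evidence. Study 1.2 compares two non-zero beats at equal carrier power, and Study 1.3 compares 20 Hz with another non-zero beat in the dorsal ACC. This also stands, in part. A difference between beat frequencies would be separate evidence of beat dependence, but if both have the same effect, the comparison cannot tell beat from carrier. Study 1.1 remains the only direct zero-beat control in Aim 1.

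Third, the full range needs equal fields along the direction considered, locked channels, and a phase at one extreme. That is correct. The documents support none of these specifically, and the simulation appears only as a figure. Study 1.1 also follows the published pilot protocol, so the settings may be recorded there. The point is that they are not stated in these documents.

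A reader might infer that the carrier field itself can reach 200% of TI's. It cannot: 200% is power, and the field reaches at most 141% as RMS and 100% as peak. A reader might also infer that the mismatch is greatest at the target, but the text gives no field data there.

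**Conclusion.** The point holds in limited form. Delivered current is matched, but a matched carrier field at the target is not assured. If the channels are phase-locked and their fields equal along a direction, control power there can be 0% to 200% of TI's. The range is 20% to 180% at a 2:1 ratio, total power varies less when the fields are not aligned, and the mismatch averages out under free drift. Phase, polarity, locking, field ratio and angle are all assumptions. If phase and polarity are constant over the 30 subjects, the mismatch is systematic, and the 20 Hz versus 0 Hz comparison cannot alone exclude a carrier explanation.

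Two stronger readings are not supported. One is that Study 1.1 fails to control for the carrier at all; it does control the current delivered. The other is that a false attribution to the beat is near certain. Any such error rate needs an effect size, which 6.0 Statistical Analysis and Sample Size does not state, together with a BOLD effect due wholly to the carrier and linear in power, and a control near antiphase. It would be a worst-case illustration, not a property of this trial.

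**What to change.** In Study 1.1:

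- Swap the two leads of one electrode pair for the whole session in half the subjects, balanced against block order. This leaves the TI condition unchanged apart from the starting phase of the beat.
- Include polarity as a factor in the 20 Hz versus 0 Hz model. A polarity effect in the zero-beat blocks would point to a carrier effect.
- Make one bench recording of both outputs to establish whether they are phase-locked and at what offset.
- Report the modelled carrier field at the target, as RMS and as peak, for both conditions.

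This needs no extra subjects, scans or scanner time. It has limits. Balancing matches carrier power only on average over subjects and not peak field. It relies on a stable phase, and it balances the BOLD response exactly only if that response is linear in power. The polarity test compares about 15 with 15 subjects (30/2) and will have low power.

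A fixed phase offset between channels is an option for the investigators to weigh. For equal aligned fields no single phase matches both measures: 90 degrees matches power but gives 71% of TI's peak.

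Without balancing or a documented phase, limit the conclusion to matched delivered current. This should be settled before data collection, because a phase that was not recorded cannot be recovered.
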